5.4 Relevance of the Results in the Light of Previous / External Data

The ARGOS-IO device performed well in patients with a Boston Keraprosthesis and showed an overall good consistency between the telemetric IOP and finder palpation/manometry. Though the implantation of the ARGOS-IO device in conjunction with the BKPro might pose additional risks compared to stand-alone BKPro implantation, the complications observed where found to be in the range of the occurrences reported in the literature. Considering the high prevalence of preexisting glaucoma in patients undergoing the Boston Keratoprosthesis surgery (Ahmad S. M. P., 2016) and the Glaucoma progression after implantation of the BKPro (de Oliveira L. A., 2014) (Samarawickrama C., 2018), the implantation of a monitoring device (ARGOS-IO) clearly outweighs the risks induced by implantation of an additional device within the same surgical procedure.

5.5 Risk / Benefit Assessment

Glaucoma is the most significant cause of the loss of regained vision in keratoprosthesis recipients. Reduction of IOP is to date the only proven therapy for glaucoma (Quigley, 2011). Improved control of IOP is linked to better long-term outcomes for glaucoma patients (King, Glaucoma, 2013).

The presence of BI-KPro does not allow conventional tonometric IOP measurement, as this requires a normal cornea. Patient self-monitoring or home measurement is also not possible, as available devices are also using tonometric IOP measurement methods. Currently, surgical manometry – if properly performed – is the only accurate means of measuring IOP in BKPro recipients. But due to its invasiveness and risk for complications, most ophthalmologists don't perform surgical manometry at BI-KPro patients. Equipment for surgical manometry is in general not available either, which is another reason why invasive IOP measurements are performed only in very rare cases. Usually finger

 Implantata Ophthalmic Products GmbH	Clinical Investigation Report ARGOS-KP01	Revision A Page 100 of 114
--	---	-----------------------------------

palpation is applied to estimate IOP, but is highly dependent on the skill of the individual examiner, provides highly subjective values and thus prone to error.

IOP in BI-KPro patients can be extremely high, potentially causing severe glaucomatous damage in unusually short periods of time. Even a comprehensive follow-up schedule may not be appropriate. This problem is compounded if no physician experienced in the finger palpation technique is available to perform IOP estimation.

The ARGOS-IO device allows frequent, reproducible IOP monitoring in both the clinical and home setting, facilitating the management of IOP in this vulnerable patient group. In addition, because of the ease of its use, it will also permit detection of fluctuations in IOP resulting from the patient's daily activities and circadian rhythm.

One objective of this study was to verify the device's accuracy in the patient population. Patients will benefit from a continual long-term monitoring of IOP independent from visits to the ophthalmologist. The Sponsor plans to develop an internet platform that will permit the physician to remotely access information from individual readings, allowing patients' IOP to be monitored by the treating physician between office visits. This will permit a more rapid response to changes in IOP and a better fine-tuning of treatment protocols.

Because of the high risk of critically IOP values possible in BKPro patients, glaucoma may progress more rapidly as at open angle glaucoma patients, which requires an even closer monitoring regimen. An additional effect may be improved adherence to prescribed treatment regimens. The potential consequences of poor IOP control are serious and can lead to irreversible loss of vision and accompanying handicap. Patient self-measurement is expected to motivate better compliance with the treatment regimen, thereby facilitating improved IOP control and optimizing long-term outcome.

The ARGOS-KP01 clinical trial was conducted to address these questions:

Compatibility with Boston-Keratoprosthesis

The ARGOS-KP01 study confirmed that it possible to implant a BKPro and ARGOS-IO sensor without mutual interference.

Irritation, Inflammation of Eye, Iris Pigment Abrasion

Does the implant cause irritation, inflammation and pigment abrasion?

 Implantdata Ophthalmic Products GmbH	Clinical Investigation Report ARGOS-KP01	Revision A Page 101 of 114
---	---	-----------------------------------

- Implant surface material has history as IOL material for ocular implantation, with well-known biocompatibility properties; material surface is soft, edges are rounded and smooth, possible small material flashes are soft and atraumatic
- In ARGOS-KP01 trial, the ARGOS-IO device was found to be safe and well tolerated within the eye. No higher levels of irritation, inflammation and pigment abrasion were observed compared to standard Boston Keratoprosthesis implantation and were manageable under standard of care.

Accuracy, precision and sensor drift

Does the ARGOS-IO device exhibit acceptable levels of accuracy and precision?

- Accuracy, precision and sensor drift have been tested and validated in bench tests and in animal trials
- The ARGOS-IO device was compared to finger palpation (the current gold standard in BI-KPro patients) within this clinical trial and showed a positive statistically significant difference of telemetric IOP measurements between the finger palpation categories (soft hypertonic, normal, borderline, hypertonic).
- ARGOS-KP01 trial has shown that the human anatomy does not have an impact on the accuracy of the device. It is recommended to re-calibrate the device once a year and following ocular surgery.

Usability

The patient acceptance of the ARGOS-IO system at home was very good, showing a very high overall acceptance in using the ARGOS-IO system in their daily routine. The instruction for use for the Mesograph reader device was easily to understand, the implant did not cause them any problems and the patients were less concerned about unidentified high IOP.

Compatibility of the ARGOS-IO implant with Glaucoma drainage devices (GDD)

Compatibility of the ARGOS-IO implant with Glaucoma drainage devices (GDD) was an issue that was long discussed within the risk analysis team. This clinical trial showed if the GDD is placed in the anterior chamber, there is no physical contact with the ARGOS-IO implant, which is located in the ciliary sulcus, and consequently no interference occurs between the two devices.

 Implantdata Ophthalmic Products GmbH	Clinical Investigation Report ARGOS-KP01	Revision A Page 102 of 114
---	---	-----------------------------------

Overall Summary: Based on the clinical study results, risk management effort and user information, it is concluded that the benefits for a patient from the implantation of an ARGOS-IO implant device outweighs the risk. Predicate implantable ophthalmic medical devices, like Boston-Keratoprosthesis, show that there is also residual risk with regard to the surgical procedure in general. The adverse event rate by combining BKPro implantation with EYEMATE-IO/KP insertion is similar to BKPro implantation alone and adverse events were in general manageable under standard of care. **The medical benefit of the implantation of the device, and resulting possibility of direct IOP measurement and frequent self-tonometry by the patients at home clearly outweighs the identified residual risks of the device. The residual risks and their probability of occurrence are within the acceptable range, compared to similar marketed devices in the ophthalmic field.**

Being able to monitor IOP quasi-continuously over extended periods of time will give the treating ophthalmologists valuable information about the individual disease of a patient and the effectiveness of the medication regimen. Most importantly, it will alert the ophthalmologist early on in case of a critically elevated IOP. Patients treated with BKPro for corneal blindness face a significant risk to consecutively lose vision due to progressive glaucomatous damage. Continual and reliable IOP monitoring, as only possible with a telemetric sensor system, is an indispensable prerequisite for adequate glaucoma management at BKPro patients to reduce post-surgical BKPro complications and to improve chances of these patients to maintain vision.

 Implantata Ophthalmic Products GmbH	Clinical Investigation Report ARGOS-KP01	Revision A Page 103 of 114
--	---	-----------------------------------

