3.4 Treatment Allocation

This was a single-arm open-label study. No randomization and blinding/masking procedures were used in this study. To avoid bias resulting from patient selection, all consecutive patients potentially meeting the eligibility requirements were informed of the study and asked to participate. Those agreeing underwent the informed consent procedure and if they consented, was screened. All eligible patients were enrolled.

 Implantata Ophthalmic Products GmbH	Clinical Investigation Report ARGOS-KP01	Revision A Page 40 of 114
--	---	----------------------------------

Measurements of IOP with the ARGOS-IO sensor was compared to IOP measured with surgical manometry in the same subject at the same time point to allow assessment of performance.

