Corneal neovascularisation	1	7.7	1
Corneal perforation	1	7.7	1
Erythema of eyelid	1	7.7	1
Eye inflammation	1	7.7	1
Eye pruritus	1	7.7	1
Keratic precipitates	1	7.7	1
Lacrimation increased	1	7.7	1
Lens disorder	1	7.7	1
Ocular discomfort	1	7.7	2
Pigment dispersion	1	7.7	1
Retinal disorder	1	7.7	1
Retinal haemorrhage	1	7.7	1
Retinal scar	1	7.7	1
Retinal tear	1	7.7	1

 Implantata Ophthalmic Products GmbH	Clinical Investigation Report ARGOS-KP01	Revision A
		Page 79 of 114

Retinal thickening	1	7.7	1
Subretinal fibrosis	1	7.7	1
Trichiasis	1	7.7	2
Visual impairment	1	7.7	1
Vitreous haemorrhage	1	7.7	1
Vitreous opacities	1	7.7	1
Gastrointestinal Disorders	2	15.4	2
Constipation	1	7.7	1
Nausea	1	7.7	1
General Disorders and Administration Site Conditions	3	23.1	4
Atrophy of the donor cornea	1	7.7	1
Leakage between keratoprosthesis and keratoplasty	1	7.7	1
Subjectively worse impression	1	7.7	1
Drug intolerance	1	7.7	1
Infections and Infestations	3	23.1	3
Bacterial disease carrier	1	7.7	1
Gastroenteritis	1	7.7	1
Urinary tract infection	1	7.7	1
Injury, Poisoning and Procedural Complications	4	30.8	8
Procedural Pain	3	23.1	3
Hyphaema	1	7.7	1
Post procedural complication	1	7.7	1
Post procedural haemorrhage	1	7.7	1
Suture related complication	1	7.7	1
Corneal graft melt	1	7.7	1
Investigations	8	61.5	35
Intraocular pressure increased	8	61.5	30
Intraocular pressure decreased	3	23.1	4
Seidel Test positive	1	7.7	1
Musculoskeletal and Connective Tissue Disorders	1	7.7	3
Back pain	1	7.7	1
Bone pain	1	7.7	1
Fibromyalgia	1	7.7	1
Nervous System Disorders	3	23.1	4
Dizziness	1	7.7	1
Headache	1	7.7	1
Paraesthesia	1	7.7	1
Syncope	1	7.7	1
Product Issues	8	61.5	13
Retroprosthetic membrane	6	46.2	7
Device material opacification (BkPro and IOL)*	3	23.1	5
Dislocation of ARGOS-IO sensor	1	7.7	1

 Implandata Ophthalmic Products GmbH	Clinical Investigation Report ARGOS-KP01	Revision A Page 80 of 114
--	---	------------------------------

Psychiatric Disorders	1	7.7	1
Panic attack	1	7.7	1
Renal and Urinary Disorders	1	7.7	2
Renal failure	1	7.7	2
Surgical and Medical Procedures	6	46.2	12
Corneal sutures removal	5	38.5	8
Corneal transplant	2	15.4	4
Vascular Disorders	1	7.7	1
Hypertension	1	7.7	1
Source: Final Statistical Output – Tables			
Table 14.3.1.3 – Adverse Events by SOC and PT: first 4 weeks, 16 weeks, 28 weeks, 12 months following implantation surgery			
%: Percentage based on N			
N: Number of subjects in total (Safety Set)			

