5 DISCUSSION

5.1 Limitations of the Study

Several aspects of the study limited its conclusiveness.

1. Only 12 patients were included and only 9 patients finished the study, which is sufficient to detect problematic design features that lead to common adverse events and still limits the number of patients that could potentially be harmed due to unforeseen events. However, with this low number of patients it is unlikely to detect rare negative effects particularly with regard to the different underlying diseases of these patients and different indications for the Boston-Keratoprosthesis implantation.
2. 12 months follow-up for a device intended for permanent implantation are too short to detect any long-term complications or late device deficiencies in patients with Boston Keraprosthetic. Since the device itself is technical identical to the CE approved EYEMATE-IO device, to be placed into the posterior chamber/ciliary sulcus of the eye during cataract surgery and this device performs well for more than several years, no main device related issues are to be expected.
3. Although surgical manometry is the only available method to accurately measure IOP in BKPro patients, it carries problems in the performance and therefore some limitations for the comparability with ARGOS-IO measurements:
 - a. Due to the puncture of the bulbus and following removal of the needle, aqueous humor can be lost which lead to a decrease of the intraocular pressure.
 - b. The quality of the measurements can be strongly influenced by experience of the investigator.

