7.9. Other Baseline Characteristics

Regarding female patients, childbearing potential and the result of a urine pregnancy test before investigational device implantation will be listed in a patient data listing.

8. Clinical Investigation Treatments**8.1. Findings Associated with Surgery**

The following descriptive statistics will be presented for each analysis population:

Statistical Analysis Plan

Version 1.0 [Final], 09-Jan-2018

- A frequency table regarding intraocular lens (IOL): patient pseudophakic (yes, no), IOL location (posterior, other location), disposition of IOL (removed, remained in eye)
- A frequency table regarding iridectomy: iridectomy performed (yes, no), method (manual, laser), location
- A frequency table regarding glaucoma drainage device (GDD): GDD in situ at start of surgery (yes, no), GDD left in place (yes, no), GDD implanted during surgery (yes, no), GDD now (yes, no), location of GDD (superior 12 o'clock, nasal, inferior 6 o'clock, temporal)
- A frequency table regarding keratoprosthesis device: implanted (yes, no)

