13.4. Table of Patient Data Listings

[To be included in Appendix 16.2 of CIR]

The numbering of data listings follows the ICH E3 guideline.

Listing	Title	Analysis Population
16.2.1.1	Patient Disposition	Screened patients
16.2.1.2	Patient Disposition after Start of Surgery	Treated patients
16.2.1.3	Patient Summary	Treated patients
16.2.2	Protocol Deviations	Treated patients

Statistical Analysis Plan

Version 1.0 [Final], 09-Jan-2018

Listing	Title	Analysis Population
16.2.3.1	Patients Excluded from Analysis Sets	Treated patients
16.2.3.2	Description of Inclusion and Exclusion Criteria	-
16.2.3.3	Fulfilment of Inclusion and Exclusion Criteria	Eligible patients
16.2.4.1	Demographic Data	Eligible patients
16.2.4.2	Disease Characteristics concerning Study Eye	Eligible patients
16.2.4.3	Baseline Ophthalmic Examinations - Anterior Eye Segment	Eligible patients
16.2.4.4	Anterior Eye Segment Findings prior to Surgery	Eligible patients
16.2.4.5	Baseline Ophthalmic Examinations - Posterior Eye Segment	Eligible patients
16.2.4.6	Posterior Eye Segment Findings prior to Surgery	Eligible patients
16.2.4.7	IOP Measurements (Goldmann Applanation Tonometry, pneumotonometry) at Screening Visit	Eligible patients
16.2.4.8	Medical History and Concomitant Diseases	Eligible patients
16.2.4.9	Prior/Concomitant Medication	Eligible patients
16.2.5.1	Implantation Surgery Data	Treated patients
16.2.5.2	ARGOS-IO Implantation	Treated patients
16.2.5.3	Intraoperative Complications	Treated patients
16.2.5.4	Status of KPro Device and ARGOS-IO Sensor after Surgery	Treated patients
16.2.6.1	IOP Measurements by ARGOS-IO and Manometry	Treated patients
16.2.6.2	IOP Measurements by ARGOS-IO and Finger Palpation	Treated patients
16.2.6.3	Device Deficiencies	Treated patients
16.2.7.1	Adverse Events	Treated patients
16.2.7.2	Serious Adverse Events	Treated patients
16.2.7.3	Adverse Device Effects	Treated patients
16.2.7.4	Adverse Events leading to Withdrawal	Treated patients
16.2.8	Pregnancy Tests	Eligible patients
16.2.9.1	Ophthalmic Examinations after Surgery - Anterior Eye Segment	Treated patients
16.2.9.2	Anterior Eye Segment Findings After Surgery	Treated patients
16.2.9.3	Ophthalmic Examinations after Surgery - Posterior Eye Segment	Treated patients
16.2.9.4	Posterior Eye Segment Findings after Surgery	Treated patients
16.2.9.5	Visual Acuity and Perimetry	Treated patients
16.2.9.6	Status Variables concerning Adverse Events and Concomitant Medication Changes	Treated patients

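### Section 5.5 says the study confirmed that keratoprosthesis and sensor can be implanted without mutual interference, but interference was never defined, summarised or compared with stand-alone implantation

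*Protocol*

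**What the plan says.** Report section 5.5 lists questions that the trial was run to answer. Compatibility with the keratoprosthesis comes first, and the whole answer is one sentence: "The ARGOS-KP01 study confirmed that it possible to implant a BKPro and ARGOS-IO sensor without mutual interference". It gives no count, criterion or table.

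The endpoints in report 3.1.3 and SAP 3.4 are device-related serious adverse events, agreement of IOP readings, adverse events and adverse device effects, device deficiencies, user acceptance and self-measurement profiles.

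For the devices themselves, the SAP plans:

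- at surgery (SAP 8.1), "A frequency table regarding keratoprosthesis device: implanted (yes, no", and in SAP 8.2 the same yes/no item for the sensor;
- Listing 16.2.5.4, "Status of KPro Device and ARGOS-IO Sensor after Surgery", which is a listing and not a summary table;
- Table 14.2.4, device deficiencies over the first 4, 16, 28 and 52 weeks;
- Table 14.2.5, ARGOS-IO readings by visit and time point.

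On design, report 3.4 states: "This was a single-arm open-label study". On size, report 5.1 states: "Only 12 patients were included and only 9 patients finished the study". The adverse event tables nevertheless use a Safety Set of 13. Table 9 includes "Dislocation of ARGOS-IO sensor" (1 patient, 1 event) and "Leakage between keratoprosthesis and keratoplasty" (1 patient, 1 event).

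**The concern.** To say that a study confirmed the absence of interference, one needs a definition of interference, an estimate of how often it occurred, and either a comparator or a limit below which it counts as absent. None of these is in the plan. The SAP is descriptive throughout, with no tests and no formal sample size calculation.

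The claim concerns a second, permanent implant in the same eye, and it stands among the answers that lead to the favourable benefit-risk summary closing section 5.5. A reader would take it as a study result, when it is a judgement with no analysis behind it.

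**Working it through.** **1. The claim beside the report's other statements**

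| Place in the report | What it says, in substance |
|---|---|
| 5.5, compatibility | No mutual interference, confirmed |
| 4.8.1, before Table 10 | An event often cannot be assigned to one of the two procedures, because both implants were placed in one operation |
| 4.8.1, device effects | A sensor contribution to retroprosthetic membrane cannot be excluded |
| Table 11 | One retroprosthetic membrane counted as an adverse device effect, not recovered |
| 5.2 | Causality cannot be clearly divided between the two implants |
| 5.4 | Adding the sensor might carry risks beyond stand-alone keratoprosthesis implantation |

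The first row cannot stand with the others. If the effects of the two devices cannot be separated, the absence of an effect of one on the other has not been confirmed.

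**2. Reproducing Table 9 (N = 13)**

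1/13 = 7.7%, 6/13 = 46.2%, 3/13 = 23.1% and 8/13 = 61.5% all match the printed percentages. The events under Product Issues add up: 7 + 5 + 1 = 13.

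**3. Intervals by the plan's own method**

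The two-sided 95% Clopper-Pearson limits for x events in n patients are: lower = the 2.5% quantile of Beta(x, n − x + 1); upper = the 97.5% quantile of Beta(x + 1, n − x). For x = 0 the upper limit is 1 − 0.025^(1/n).

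| Event | Patients | % (95% CI) | Table 10 (procedure-related) | Table 11 (device-related) |
|---|---|---|---|---|
| Sensor dislocation | 1/13 | 7.7 (0.2 to 36.0) | yes, outcome recovered | no |
| Leakage between keratoprosthesis and graft | 1/13 | 7.7 (0.2 to 36.0) | no | no |
| Retroprosthetic membrane | 6/13 | 46.2 (19.2 to 74.9) | 5 patients | 1 patient |
| Opacification of keratoprosthesis or IOL | 3/13 | 23.1 (5.0 to 53.8) | 3 patients | no |

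Of the five opacification events, four were on the keratoprosthesis and one on an IOL (Table 9 footnote). With 12 recipients as denominator, dislocation is 1/12 = 8.3% (0.2 to 38.5).

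**4. What a result of no events could have shown**

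- 0/13: 1 − 0.025^(1/13) = 24.7%
- 0/12: 1 − 0.025^(1/12) = 26.5%
- 0/9 (completers): 1 − 0.025^(1/9) = 33.6%

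The chance of seeing at least one case in 13 patients is 1 − (1 − p)^13. That is 48.7% for a true rate of 5%, 74.6% for 10% and 94.5% for 20%. A problem affecting 1 patient in 20 would be missed about half the time.

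**5. Denominator**

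The synopsis says that 12 patients received implants. The Safety Set, defined in report 4.6 as attempted sensor implantation, is 13. The text I could read does not explain the difference.

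**The case against.** The strongest reply has four parts.

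- **Feasibility wording.** The sentence says that implanting both devices is possible, and one dislocation does not refute that. This stands. The fault lies in the claim that absence of interference was confirmed.
- **Device function was followed.** Table 14.2.5 includes the number of valid cases at weeks 4 to 52, Table 14.2.4 counts implant deficiencies, and loss or dislocation of the implant was an adverse event of particular attention. Report 4.7.1.1 says that telemetry was done at every visit of every patient. It would therefore be wrong to infer that nothing about the devices was recorded after surgery. None of these items, however, measures interference or summarises retention of both devices. Sections 4.1, 4.4 and 4.8.3 of the report, and part of 4.8.1, were not in the text I could read and may hold relevant counts.
- **Relatedness ratings.** A reader might infer from Table 9 that interference did occur, citing the dislocation, the leakage, the positive Seidel test, the corneal perforation and the corneal transplants. The documents do not support this. None of the five is in Table 11. Leakage, Seidel test and perforation are not in Table 10 either, and that table is complete: 61 + 2 + 7 + 25 + 1 + 11 + 9 = 116, its stated total. The ratings do not exclude interference, because the procedure as the report defines it covers both implantations.
- **Disclosure.** The report admits the small sample and the unresolved causality. This is true, and it is why the unqualified sentence in 5.5 is inconsistent with the rest.

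It is also fair to say that a retention table without a control arm cannot test interference.

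**Conclusion.** The conclusion in 5.5 is unsupported as worded and conflicts with report sections 4.8.1, 5.2 and 5.4. Interference was not a defined endpoint, retention of the two devices has no planned summary, and there was no stand-alone arm. The data are compatible both with no interference and with a substantial rate: the upper limit is 36.0% for the one observed dislocation, and would be 24.7% with no event at all in 13 patients.

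This rests on the endpoints and the SAP's table list, both of which are visible, and on treating patients as independent with the stated denominators. It is not a finding that the devices interfere. Nor does the gap between 12 and 13 show that a sensor implantation failed; the documents leave it unexplained. No primary or secondary endpoint result changes.

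**What to change.** Replace the sentence in 5.5 with:

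1. the number of patients in whom both devices were implanted, reconciling 12 with 13;
2. the dislocation and the keratoprosthesis-related events, with Clopper-Pearson intervals and their device and procedure relatedness ratings;
3. a statement that interference was not a defined endpoint, was not compared with stand-alone implantation and cannot be excluded.

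Support it with one descriptive table of patients with the keratoprosthesis in place, and with the sensor in place and readable, at weeks 4, 16, 28 and 52. The sources are Listing 16.2.5.4, the adverse event listing and the valid counts in Table 14.2.5. Give the number of patients still under follow-up at each week. Label the table post hoc, since the SAP was final in January 2018, and present it as description and not as a test of interference. The title of Listing 16.2.5.4 does not show whether it covers later visits; if it does not, the in-place counts must come from the other sources.

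The cost is one table from data already collected and a less favourable sentence.
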